3.1 Research Design

This study is a multi-center cooperative study of the South China Neonatal Genetic Screening Alliance. The principal investigator (PI) and project leader of this study are [name], chief physician of pediatrics of the Sixth Affiliated Hospital of Sun Yat-sen University, who plans to include 123 cooperative units of the South China Neonatal Genetic Screening Alliance. In this study, 40,000 neonatal genetic screening data and MS / MS data were retrospectively analyzed through multi-center cooperation. The collection date was from January 2019 to August 2022.

Through the statistical analysis of neonatal genetic screening data (138 genes related to 133 common genetic diseases), the incidence of common genetic diseases in newborns in China, the carrying rate of pathogenic variation and the high-frequency variation sites of the population were clarified, and the epidemiological characteristics of newborns in China were studied.

Through the statistical analysis of neonatal genetic screening data and MS / MS metabolomics data (11 amino acids and 28 acylcarnitines), the correlation between gene and metabolism will be explored, and the pathogenicity of high-frequency VUS mutation sites will be identified by using protein function artificial intelligence analysis platform and tandem mass spectrometry metabolite data.

The prediction model of common genetic diseases is constructed by using machine learning algorithms such as random forest, support vector machine, elastic network and multi-layer perceptron, so as to realize the accurate diagnosis of common genetic diseases through tandem mass spectrometry metabolomics data, and expand 2-3 kinds of diseases that can be detected by MS / MS technology.

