model was applied to the diagnosis of common pediatric diseases. The results showed that the diagnostic accuracy of 55 common pediatric diseases was close to 90 %. Some diseases such as acute upper respiratory tract infection had a diagnostic accuracy of 95 %, and the average score of the artificial intelligence model was higher than that of the doctor group. Therefore, artificial intelligence can assist early disease diagnosis through a large amount of medical data, improve diagnosis efficiency and reduce misdiagnosis rate, solve the problem of insufficient medical service capacity to a certain extent, and improve the fairness and accessibility of health services. In the field of neonatal disease screening, with the promotion of genetic screening technology and the inclusion of more genetic metabolic diseases in screening, accurate and rapid judgment of multiple disease risks has become an urgent need for clinical front-line. Artificial intelligence has obvious advantages in the interpretation and risk prediction of genetic metabolic disease gene results, which not only significantly reduces the false positive results and saves medical resources ; for areas with weak clinical foundation and urgent need to carry out neonatal genetic metabolic disease gene screening projects, artificial intelligence tools will become a strong support for clinicians, promote the standardization and standardization of genetic metabolic disease diagnosis, and improve the efficiency and accuracy of neonatal genetic metabolic disease gene screening system.

According to the preliminary development of neonatal genetic screening in China, we will retrospectively collect and analyze the genetic screening data and tandem mass spectrometry data of 40,000 newborns in the participating units of the South China Neonatal Genetic Screening Alliance, so as to understand the incidence of neonatal genetic diseases in China and the characteristics of the carrying rate and mutation sites of related gene pathogenic variations, and provide scientific research basis for the feasibility, clinical value and social benefits of large-scale genetic screening. In addition, our previous studies have found that the mutation sites with high carrying rate (more than 1 %) in many populations are mutations of unknown clinical significance (VUS). The pathogenic interpretation of such mutations has brought serious confusion to clinicians and brought pending trouble to the subjects.

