1.2 Creativity

This study is a multi-center cooperative study of the South China Neonatal Genetic Screening Alliance. Through the analysis of 40,000 cases of neonatal genetic screening data and MS / MS data, the incidence of common genetic diseases in newborns in China and the carrying rate of related gene pathogenic mutations are deeply understood, and the types of diseases, gene selection, gene screening process, interpretation of gene screening results, follow-up and treatment of screening positive patients and other related contents of neonatal genetic screening are preliminarily clarified, so as to provide scientific research basis for the feasibility, clinical value and social benefits of large-scale genetic screening.

In addition, this study will clarify the correlation between genotypes and metabolic profiles of common genetic diseases in newborns, and explore the feasibility of using protein function artificial intelligence analysis platform and tandem mass spectrometry metabolite data to accurately predict the pathogenicity of

ectopic sites of genetic metabolic lesions through protein function prediction and metabolic level analysis of high-frequency mutation sites of genes, that is, to solve the pathogenicity of mutations with unknown clinical significance. It will also expand the types of disease diagnosis of neonatal MS / MS technology.

This study will also establish a risk assessment model for neonatal genetic metabolic disease gene screening results through artificial intelligence methods. By identifying the pathogenicity of mutation sites, especially those with unclear clinical significance, it can quickly identify high-risk children and reduce false positive rates, thereby improving the accuracy and system efficiency of neonatal genetic screening.

2. Research objective

(1) Gene sequencing data (138 genes related to 133 common genetic diseases) and tandem mass spectrometry metabolomics data (11 amino acids and 28 acylcarnitines) of about 40,000 newborns from the South China Neonatal Genetic Screening Alliance participating units were collected and collated to complete the database construction of genes and mass spectrometry.

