(2) A retrospective analysis of the incidence, pathogenic mutations, suspected pathogenic mutations, and the carrying rate of unexplained mutations of 133 common neonatal genetic diseases in 40,000 cases was conducted, and the distribution of high-frequency variation sites in the population was counted, providing a scientific basis for the selection of mutation sites for large-scale genetic screening of neonatal genetic diseases.

(3) Protein function prediction and enzyme catalytic activity analysis were performed on high-frequency mutation sites of genetic metabolic diseases (IEM). Characteristic metabolites were analyzed and verified for mutation sites with low enzyme catalytic activity. The feasibility of using protein function artificial intelligence analysis platform and tandem mass spectrometry metabolite data to accurately predict the pathogenicity of genetic metabolic lesions was explored.

(4) Explore the use of genome and metabolome big data and machine learning algorithms such as Random forest, Support Vector Machine, Elastic net, Multilayer Perceptron to construct prediction models for common genetic diseases, and strive to achieve accurate diagnosis and prediction of common genetic diseases using simple

tandem mass spectrometry metabolome data, and expand the application range of tandem mass spectrometry technology for disease detection.

3. Research scheme and technical route

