0.001-0.01), benign (B, pathogenic possibility < 0.001). The results of gene detection in this study only classified pathogenic and possible pathogenic mutations as positive mutations, and homozygotes and compound heterozygotes of autosomal recessive inheritance, single heterozygotes and homozygotes of autosomal dominant inheritance, and hemizygotes of X-linked inheritance were classified as disease positive. The unclear clinical significance is not directly used as the basis for clinical diagnosis. It is necessary to combine the clinical, if necessary, to carry out the corresponding family member verification, auxiliary examination, clinical follow-up.

(3) MS / MS data collection and standardization : The collected data include (1) laboratory background information including instrument type, reagent type, quality control material type, laboratory quality control rules, filter paper type, normal population range ; (2) Quality control data included quality control number, quality control type, quality control batch number, amino acid internal standard batch number, acylcarnitine internal standard batch number, factory time, experimental time, and test value of each quality control analyte ; (3) Screening test data include screening number, gestational age, breastfeeding method, native place (province, city), newborn gender, birth date, birth weight, sample number, blood collection time, etc. ; (4) The data of confirmed cases included screening number, confirmed disease, blood ammonia test, blood gas analysis, blood routine, liver function test, urine GC-MS test, imaging examination, gene detection information and other tests. The fluctuation range of the detection concentration of the corresponding batch of quality control samples was within the target value ± 3 s. Finally, the data were collected and sorted into the negative database and the positive database. In order to eliminate the influence of regional differences, the series detection index data were standardized.

(4) By analyzing the correlation between large sample gene data and tandem mass spectrometry data and the correction of clinical prognosis, a neonatal genetic disease gene screening database and an artificial intelligence risk assessment

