3.6 Observation items

(1) Positive detection rate of common genetic diseases in neonates : the results of genetic testing of enrolled neonates showed that the proportion of homozygous and compound heterozygotes of autosomal recessive inheritance, single heterozygote and homozygous of autosomal dominant inheritance, and hemizygote of X-linked inheritance accounted for the total number of people tested.

(2) The corresponding pathogenic genes and pathogenic variation carrying rate of common neonatal genetic diseases : that is, the proportion of the total number of occurrences of pathogenic variation, suspected pathogenic variation and

unknown clinical significance variation in the genetic test results of the enrolled neonates according to the ' ACMG genetic variation classification criteria and guidelines ' and ' genetic variation classification criteria and guidelines (2017) '.

- (3) The carrying rate of high-frequency mutation sites in the population : that is, the mutation sites with a population carrying rate greater than 1 %.
- (4) Establish a complete protein structure and catalytic activity analysis process, and develop artificial intelligence protein analysis tools for pathogenicity prediction of mutation sites.
- (5) Preliminary identification of the pathogenicity of high-frequency VUS mutation sites : The protein structure and enzyme catalytic activity characteristics of high-frequency VUS mutation sites were predicted by artificial intelligence tools, and the metabolic spectrum differences between positive, carrier and negative samples of high-frequency VUS mutation sites were clarified by combining with tandem mass spectrometry metabolite data, which provided a basis for the pathogenicity judgment of VUS mutation.
- (6) Gene-metabolism correlation : machine learning algorithms such as random forest, support vector machine, elastic network and multi-layer perceptron are used to construct prediction models of common genetic diseases, so as to realize accurate diagnosis of common genetic diseases through tandem mass spectrometry metabolomics data, and expand 2-3 diseases that can be diagnosed by tandem mass spectrometry.

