3.7 Statistical processing

IBM-SPSS 26.0 statistical software and R language (Version 4.1.0) were used for statistical analysis of the test results, and the positive rate of neonatal genetic disease screening (common positive disease cases, common positive sites) was counted. The carrying rate of common mutation sites in newborns was counted. The measurement data were expressed as mean \pm standard deviation ($x \pm s$), and t test was used for comparison between groups. The count variables were expressed as values or rates (%), and the comparison between groups was tested. Unconditional logistic regression analysis was used to evaluate the correlation between genotype and

clinical phenotype. Generalized multifactor dimensionality reduction (GMDR) was used to analyze gene-gene interaction and genotype-phenotype correlation. Based on tandem mass spectrometry data, machine learning algorithms such as random forest, support vector machine, elastic network, and multi-layer perceptron were used to construct genotype prediction models. Accuracy, Balanced accuracy, sensitivity, and specificity were used to evaluate the prediction effect of the model.

4. Ethics in clinical research

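### Sections 1.1, 1.2 and 3.1 promise the incidence of genetic disease in newborns in China, but the only disease-level rate defined is genotype-positives among 37–42-week newborns given both tests at South China alliance units

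*Combined protocol and SAP*

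**What the plan says.** Three sections state a national disease target. Section 1.1 says the data will be collected "so as to understand the incidence of neonatal genetic diseases in China". Section 1.2 says that "the incidence of common genetic diseases in newborns in China and the carrying rate of related gene pathogenic mutations are deeply understood". Both name the genetic and the MS/MS data as the source. Section 3.1 (Research Design) relies on the genetic screening data alone: it says they will clarify "the incidence of common genetic diseases in newborns in China, the carrying rate of pathogenic variation", and adds that "the epidemiological characteristics of newborns in China were studied". Objective 2, in section 2 and in the Abstract, is narrower. It opens with "A retrospective analysis of the incidence, pathogenic mutations, suspected pathogenic mutations" and confines the work to the 40,000 cases.

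The measures are set out in 3.6 and 3.7. Item 1 of 3.6 defines a positive detection rate. Its numerator is newborns with a disease-positive genotype under recessive, dominant or X-linked rules, and its denominator is everyone tested ("hemizygote of X-linked inheritance accounted for the total number of people tested"). Section 3.7 plans to count "the positive rate of neonatal genetic disease screening" and the carrying rate of common sites. Section 3.3 item 2 fixes which variants count: "The results of gene detection in this study only classified pathogenic and possible pathogenic mutations as positive mutations". Item 1 of 3.6 does not repeat that limit.

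Section 3.4 admits newborns of 37–42 weeks who had genetic screening and MS/MS at the same time. The records come from 123 alliance units, January 2019 to August 2022.

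**The concern.** Incidence of disease needs affected newborns in the numerator and the births of a defined population in the denominator. The plan defines neither. Its one disease-level rate counts genotypes, in a group selected by gestation, by having had both tests, and by attending an alliance unit. The label positive detection rate is accurate for that quantity. The difficulty is that 1.1, 1.2 and 3.1 attach a different quantity and a different population to the result.

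This matters because incidence is among the results that 1.1 and 1.2 offer as a basis for large-scale genetic screening. A report that follows the plan would present a genotype-positive rate from one alliance as disease incidence in China. A larger sample would not cure this.

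**Working it through.** The 40,000 has no stated precision, expected rate or power behind it, so there is no figure of the plan's own to reproduce. The check is a comparison of passages, with arithmetic for scale only.

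**Step 1. Target against measure.**

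| Element | Stated target (1.1, 1.2, 3.1 Research Design) | Defined measure (3.3, 3.4, 3.6, 3.7) |
|---|---|---|
| Numerator | Newborns with genetic disease | Newborns with a P/LP disease-positive genotype |
| Denominator | Newborns in China | Newborns of 37–42 weeks with both tests at alliance units |
| Link to births | Implied | No birth denominator, no weighting |
| Regional adjustment | Needed for a national figure | In 3.3 item 3, applied to MS/MS index values, not to rates |

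**Step 2. Could other planned data fill the gap?** Section 3.3 item 3 collects confirmed disease, and the Abstract lists clinical, biochemical and imaging data for positive samples. No rate in 3.6 or 3.7 uses them. The free sequencing in 4.3 verifies the genotype, not the disease.

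**Step 3. Why the direction is open.** Let g be the genotype-positive rate, v the share of genotype-positives with disease, and m the disease frequency among genotype-negatives (for example, newborns carrying only variants of unknown significance). Disease frequency among those tested is

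d = g·v + (1 − g)·m.

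So g overstates d if g(1 − v) > (1 − g)m, and understates it if the inequality is reversed. The documents give neither v nor m.

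**Step 4. Illustration of scale (v assumed).** The positive rates are those cited in 1.1, from other panels or an earlier study. The last column is g·v, the contribution of genotype-positives only.

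| g | Positives in 40,000 | Confirmed at v = 25 / 50 / 75% | Share of all tested |
|---|---|---|---|
| 2.3% | 0.023 × 40,000 = 920 | 230 / 460 / 690 | 0.6 / 1.2 / 1.7% |
| 4.0% | 0.04 × 40,000 = 1,600 | 400 / 800 / 1,200 | 1.0 / 2.0 / 3.0% |
| 8.81% (team's Guangdong study, as stated) | 0.0881 × 40,000 = 3,524 | 881 / 1,762 / 2,643 | 2.2 / 4.4 / 6.6% |

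**Step 5. Sample size is not the remedy.** Treating newborns as independent, the 95% half-width is about 1.96 × √(g(1 − g)/40,000), which is 0.15, 0.19 and 0.28 percentage points for the three rates. The cited rates differ by 8.81 − 2.3 = 6.51 points, more than 20 times the largest half-width (6.51/0.28 ≈ 23). Panels and methods differ between those studies, so the spread is not a regional effect alone. It shows only that who is tested and what counts as positive can matter far more than n.

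**The case against.** The strongest reply is that the plan does have an operational disease definition. Section 1.1 calls gene detection the gold standard for diagnosing most genetic diseases, and 3.3 item 2 classes the listed genotypes as disease positive. Read this way, the positive detection rate is the incidence measure. The reply has some force for the numerator, but it does not settle it: 1.1 and 1.2 themselves aim to lower the false positive rate of gene screening, so the protocol accepts that a positive genotype need not mean disease. It does nothing for the denominator, because no passage supports the step from alliance units to China.

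Three further points stand. Objective 2 is confined to the 40,000 cases, so the national wording lies in the background, the novelty section and 3.1. Only 3.1 rests incidence on gene data alone; 1.1 and 1.2 name both data types. And the planned calculation is correct under its own label, so the change needed is to what is claimed for it.

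A reader might infer that the exclusion of newborns outside 37–42 weeks produces an undercount. It does not follow: those newborns are absent from the denominator as well, and the documents do not say that disease frequency differs by gestation. The restriction limits generalisability.

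**Conclusion.** The mismatch holds. As written, the plan yields the prevalence of P/LP disease-positive genotypes in a selected sample, and neither disease incidence nor a figure for China follows from it.

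The size and direction of the error cannot be computed from the documents. A reader might infer from Step 4 that incidence will be overstated. That is not supported: the shares are assumed, and disease among genotype-negatives is left out of the table. Nor does the point undermine the study as a whole, because the variant-frequency aims within the tested sample do not depend on incidence.

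One assumption is that the region is South China. This is inferred from the alliance name; the documents do not list the provinces of the units.

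**What to change.** 1. In 1.1, 1.2, Objective 2 (section 2 and Abstract) and 3.1 Research Design, replace incidence with: prevalence of P/LP disease-positive genotypes among 37–42-week newborns tested by both methods at South China alliance units, January 2019 to August 2022. Remove the reference to China from these incidence and epidemiology statements. Use the same definition, with the P/LP limit, in 3.6 item 1.
2. Show the rates by native place (province, city), which 3.3 item 3 already collects.

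Optional: where confirmation data exist, mainly for diseases that MS/MS can screen, report by disease (a) clinically or biochemically confirmed newborns over all tested and (b) confirmed genotype-positives over all genotype-positives. Do not count a case confirmed by genotype alone. State how many positives had confirmation data and label both figures as lower bounds, because ascertainment is uneven and 1.1 notes that metabolites in some diseases are usually normal in the neonatal period. The choice of denominator matters: with 1,600 positives, 1,000 with data and 500 confirmed (all assumed), (b) is 500/1,600 = 31%, while 500/1,000 would show 50%.

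Items 1 and 2 cost wording and one table, and leave a narrower claim. The optional figures need a count at each unit of which positives have confirmation data, and may be informative only for some diseases. Confidence intervals are a separate matter and not part of this change.

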3.1 Sample size

This study plans to collect genetic screening data (138 genes related to 133 common genetic diseases) and tandem mass spectrometry metabolomics data (11

amino acids and 28 acylcarnitines) of about 40,000 newborns from January 2019 to August 2022 in 123 cooperative units of the South China Neonatal Genetic Screening Alliance.

3.3 data collection

In the course of the study, no random or any treatment driven by the research program will be performed or provided to the subjects. The researchers will view the patient 's medical history and laboratory reports, and determine the patient 's eligibility according to the inclusion and exclusion criteria.

(1) The types of diseases detected by genetic screening : including 133 kinds of hereditary diseases with high incidence in neonates. The types of diseases include genetic metabolic diseases such as amino acid metabolic diseases, organic acid metabolic diseases and fatty acid metabolic diseases within the scope of all neonatal tandem mass spectrometry screening, as well as other genetic diseases that cannot be screened by tandem mass spectrometry but have high incidence and early detection of great clinical significance and social benefits for children and families, such as lysosomal diseases, glycogen accumulation diseases, hepatolenticular degeneration, hereditary deafness, β -thalassemia, etc.

(2) In this study, the data analysis of genes and the interpretation of test reports are based on the implementation of industry consensus or guidelines for genetic testing of genetic diseases such as ' Discussion on the standardized consensus of the whole process of clinical detection of genetic diseases second-generation sequencing '. The analysis and interpretation of test data refer to the ' ACMG genetic variation classification criteria and guidelines ' issued by the American Society of Medical Genetics and Genomics (ACMG) in conjunction with the Molecular Pathology Society (AMP) and the domestic ' genetic variation classification criteria and guidelines (2017) '. The variation was divided into five grades : pathogenic (P, pathogenic possibility > 0.99), suspected pathogenic (LP, pathogenic possibility 0.95-0.99), unknown clinical significance (VUS, pathogenic possibility 0.01-0.90), suspected benign (LB, pathogenic possibility

0.001-0.01), benign (B, pathogenic possibility < 0.001). The results of gene detection in this study only classified pathogenic and possible pathogenic mutations as positive mutations, and homozygotes and compound heterozygotes of autosomal recessive inheritance, single heterozygotes and homozygotes of autosomal dominant inheritance, and hemizygotes of X-linked inheritance were classified as disease positive. The unclear clinical significance is not directly used as the basis for clinical diagnosis. It is necessary to combine the clinical, if necessary, to carry out the corresponding family member verification, auxiliary examination, clinical follow-up.

(3) MS / MS data collection and standardization : The collected data include (1) laboratory background information including instrument type, reagent type, quality control material type, laboratory quality control rules, filter paper type, normal population range ; (2) Quality control data included quality control number, quality control type, quality control batch number, amino acid internal standard batch number, acylcarnitine internal standard batch number, factory time, experimental time, and test value of each quality control analyte ; (3) Screening test data include screening number, gestational age, breastfeeding method, native place (province, city), newborn gender, birth date, birth weight, sample number, blood collection time, etc. ; (4) The data of confirmed cases included screening number, confirmed disease, blood ammonia test, blood gas analysis, blood routine, liver function test, urine GC-MS test, imaging examination, gene detection information and other tests. The fluctuation range of the detection concentration of the corresponding batch of quality control samples was within the target value ± 3 s. Finally, the data were collected and sorted into the negative database and the positive database. In order to eliminate the influence of regional differences, the series detection index data were standardized.

(4) By analyzing the correlation between large sample gene data and tandem mass spectrometry data and the correction of clinical prognosis, a neonatal genetic disease gene screening database and an artificial intelligence risk assessment

model were established. Construction and selection of modeling indicators, select core indicators through information gain and correlation coefficient, and construct combined features ; in the model training stage, the gene screening data is divided into training set and test set at a ratio of 8 : 2, and the ensemble learning models such as random forest, gradient boosting tree algorithm and artificial neural network are trained to select the best model. Model evaluation, the model selection process first meets the detection rate of 1, and then compares the false positive rate to select the optimal training model. Model verification, using a new batch of big data samples, through model calculation, output high-risk and low-risk sample lists, and compare and analyze with the original screening results.

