4.3 Benefits of participating in research

There is no direct economic benefit for all the test subjects included in this study, but for the positive children included in this study, free first-generation sequencing verification is provided, and professional genetic counseling and clinical treatment advice are provided to parents by pediatric clinicians with the consent of the parents of the children.

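### The positive detection rate counts X-linked disease in hemizygotes only, so girls with two pathogenic alleles at an X-linked gene are in the denominator but cannot enter the numerator for that disease

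*Combined protocol and SAP*

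**What the plan says.** Section 3.3 item (2) first limits positive mutations to P and LP variants, then lists the genotypes that make a newborn disease positive. The two-allele genotypes come first, as "homozygotes and compound heterozygotes of autosomal recessive inheritance". The list then closes with "single heterozygotes and homozygotes of autosomal dominant inheritance, and hemizygotes of X-linked inheritance were classified as disease positive".

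Section 3.6 item (1) turns the same list into the positive detection rate. It ends with "single heterozygote and homozygous of autosomal dominant inheritance, and hemizygote of X-linked inheritance accounted for the total number of people tested", so the denominator is everyone tested, of either sex. The inclusion criteria in 3.4 do not restrict sex. Section 3.7 plans the matching tabulation: "the positive rate of neonatal genetic disease screening (common positive disease cases, common positive sites) was counted".

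No section adds a category for girls at X-linked genes, and none limits the X-linked denominator to boys. Sex is recorded: the screening data in 3.3 item (3) include "newborn gender, birth date, birth weight".

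**The concern.** The list is specific about zygosity. It even names homozygotes for autosomal dominant disease, where one allele already suffices. The X-linked clause therefore cannot safely be read as shorthand for all affected genotypes.

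Read literally, two newborns with the same kind of genotype, two P/LP alleles at the disease gene, are treated differently. One is counted if the gene is autosomal recessive. The other is not counted if the gene is X-linked and the newborn is a girl.

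The positive detection rate is the first observation item. Where such girls are in the data, the omission can only lower the X-linked part of that rate, and a larger sample does not remove it. With 123 cooperating units supplying data, an unstated convention for girls could also be applied differently from one unit to another.

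**Working it through.** **Reading the rule.** The plan gives no figure for X-linked positives, so there is nothing of its own to reproduce. The genotypes sort as follows under 3.3(2) and 3.6(1):

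- Two P/LP alleles, autosomal recessive gene: counted.
- One or two P/LP alleles, autosomal dominant gene: counted.
- Hemizygous, X-linked gene: counted.
- Girl with two P/LP alleles, X-linked gene: not listed, but in the denominator.
- Girl with one P/LP allele, X-linked gene: not listed, but in the denominator.

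**Inputs for size.** N = 40,000 is from the plan (3.1 Sample size). The rest are assumptions: 20,000 boys and 20,000 girls, random mating, and a total P/LP allele frequency q at one X-linked gene, taken over a range.

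**Formulas.**

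- Boys counted = 20,000q.
- Two-allele girls not counted = 20,000q².
- Missed share of that gene's positives = 20,000q² / (20,000q + 20,000q²) = q/(1+q).
- Rate as written = q/2. Rate with the girls = p = (q + q²)/2. Understatement = q²/2.
- 95% half-width of that disease's rate = 1.96 × √(p(1−p)/40,000).

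| q | Boys counted | Girls not counted (expected) | Missed share | Understatement (points) | Half-width (points) | Ratio |
|---|---|---|---|---|---|---|
| 0.001 | 20 | 0.02 | 0.1% | 0.00005 | 0.0219 | 0.002 |
| 0.01 | 200 | 2 | 1.0% | 0.005 | 0.0695 | 0.07 |
| 0.05 | 1,000 | 50 | 4.8% | 0.125 | 0.1567 | 0.80 |

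At q = 0.01 the gene's rate moves from 0.500% to 0.505%. At q = 0.05 it moves from 2.500% to 2.625%.

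**Where it would matter.** Setting q²/2 equal to the half-width gives q of about 0.058. There the understatement is 0.058²/2, about 0.17 points, with about 20,000 × 0.0582 = 1,164 boys counted and 20,000 × 0.0582² = 68 girls missed.

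**Against the overall rate.** Section 1.1 quotes positive rates from 2.3% to 8.81% in other screening work. At N = 40,000 their half-widths are 1.96 × √(0.023 × 0.977/40,000) = 0.147 points and 1.96 × √(0.0881 × 0.9119/40,000) = 0.278 points. One gene's understatement is below both throughout the table.

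**Sensitivity to the sex split.** With 45% girls the missed share is 0.45q/(0.55 + 0.45q), which is 0.08%, 0.8% and 3.9% at the same three values of q.

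**The case against.** The strongest reply is that this is a wording gap with almost no numerical effect. For a gene with q = 0.001 the expected number of missed girls is 0.02, so the chance that none occurs is about e^(−0.02) = 98%, and then the observed rate is unaffected. The documents give no gene list by inheritance and no X-linked allele frequency, so nothing supports a q as high as 0.05. Section 1.1 says that many sites carried by more than 1% are of unknown significance, and 3.3(2) does not count those as positive. There is also a narrow exception to the gap: a girl with a deletion on one X and a P/LP variant on the other might be called hemizygous. All of this stands, and it sets the severity. It does not repair the definition, which leaves these girls out by its own terms.

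Three stronger readings are tempting, and the documents do not support them.

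- A reader might infer that X-linked figures are biased whatever the data show. They are understated only if such girls are among those tested.
- A reader might infer that the planned disease incidence is necessarily too low. Objective (2) plans "A retrospective analysis of the incidence, pathogenic mutations, suspected pathogenic mutations", and section 3.1 draws incidence from the genetic screening data. But neither defines incidence as the 3.6(1) rate, and 3.3 item (3) separately collects confirmed disease for confirmed cases. The documents do not say which source feeds incidence.
- A reader might infer that heterozygous girls are missed positives too, which would be a far larger loss. That needs a disease definition the sponsor did not write, for a disease the documents do not place on the panel. Under the printed list these girls are not disease positive, and their variants can still enter the carrying rate in 3.6(2). What is fair to ask is that the plan state how they are tabulated.

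**Conclusion.** The concern holds for the positive detection rate in 3.6(1) and the matching list in 3.3(2). The definition omits girls with two P/LP alleles at an X-linked gene while keeping them in the denominator. Such a girl can still be counted positive for another disease.

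The effect is negligible for rare genes and, at the frequencies tabulated, stays within sampling error for both the disease-specific and the overall rate. These sizes rest on an assumed equal sex split, random mating and assumed allele frequencies, so the actual effect cannot be determined from the documents. Severity is low: the reason to act is that the definition is incomplete as written and cheap to correct, not that the headline rate would change noticeably.

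**What to change.** For counting only:

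1. In the 3.6(1) tabulation, include girls with two P/LP alleles at an X-linked gene in the numerator for that disease.
2. Report X-linked rates separately for boys and girls, each over its own denominator.
3. State in 3.6(1) how girls heterozygous at an X-linked gene are tabulated.
4. Have the sponsor reconcile the wording of 3.3(2) with the counting definition, so that one term does not carry two meanings.

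The last step needs care because section 4.3 ties an offer to the same label: "for the positive children included in this study, free first-generation sequencing verification is provided". Nothing here proposes a change to who receives that offer. The clinical classification and the follow-up offers stay with the investigators.

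The cost is a few sentences and a re-tabulation of existing records. Sex and genotype are already collected, and the study is retrospective, so no new data are needed.
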